## **2.7. ASSESSMENT PARAMETERS AND METHODS**

### **A. Source Documents & Data Collection Methods:**

1. All data collected for this study will be collected through the sponsor's online database, Joint Assist. Centers may enter data directly to Joint Assist via any internet capable device with web browser capability. Devices that may be used include personal computers, laptops, iPads, etc. If using the paper case report forms for data entry, it will be required that the center then enter that data to Joint Assist.
2. Thorough training on Joint Assist will be completed with all investigators. Source documents that may be used include: direct entry to Joint Assist via computer or iPad, study supplied Case Report Forms which are later entered to Joint Assist, or may be medical records at the site which are also later entered into Joint Assist. A source document record should be recorded prior to study start.

### **B. Screening Log & Enrollment Form (Please also reference Section 3.3)**

#### **1. Pre-operative Screening:**

- a. Patients will be screened according to the inclusion / exclusion criteria detailed in Section 3. Patient eligibility will be documented on the screening log. A pregnancy test should be performed if necessary, and negative results on file for all female subjects unless sterilized or post-menopausal to ensure subjects are not enrolled into the study who are pregnant.

#### **2. Enrollment Form:**

- a. Patient consent, study treatment assignment, and eligibility will also be documented on an enrollment form.

**C. Center Level Information**

1. **Patient Expectations of Knee Replacement Recovery\***
  - a. Each center's standard of care method for managing patient expectations for total knee replacement recovery will be documented and sent to the sponsor.
2. **Patient Rehabilitation\***
  - a. Each center's standard of care method for patient post-operative rehabilitation for total knee replacement recovery will be documented and sent to the sponsor.

*\*Not a research intervention, will be used for data analysis only. Not patient level data, and should be a summary of what is done as standard of care for all total knee patients at the center.*

**D. Medical History and Demographic Data**

1. Demographic information will be collected. Medical history will be obtained and a physical examination will be performed (including height and weight). Current medications, diagnosis, previous surgery, contralateral knee status, and comorbidities will also be recorded. Patient contact information (mailing address, phone number, and email address) will be collected in order to administer PROMS surveys either when a patient is unable to return for a clinical exam, or after the 2-year visit when the PROMS questionnaire is the only data point required.

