### **1.4. PURPOSES**

- A. Compare patient perception of their knee implant feeling “normal / asymptomatic.”
- B. Compare clinical outcomes through 2 year standard of care follow-up.
- C. Evaluate patient perceived clinical outcomes and survivorship through 10-years of follow-up.

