**F. Clinical Outcomes**

1. Data to determine the clinical and functional performance of the device will be collected. Pre-operative and post-operative analysis will be compared using recognized and validated systems:
  - a. **Modified Knee Society Score**
    - i. The American Knee Society Score is part clinical exam and part patient administered assessment of the knee. The objective part of the score, also known as the "knee score," should be collected in the clinic by qualified personnel. The functional and pain scores can be collected in

the clinic or via phone or mailer. An additional assessment of the incidence of “anterior knee pain” has been added to this CRF as an exploratory endpoint but does not affect the score. The full score will be collected preoperatively and at each post-operative visit through 2-years. After the 2-year visit, the patient administered portion will be collected with the PROMS Questionnaire by phone, email, or mailer from the patient.

b. Patient Reported Outcome Measures “PROMS”

- i. A PROMS Questionnaire will be completed by the patient before surgery, and at each postop appointment indicated in the data collection table to assess the patient’s perception of their knee replacement. This survey can be collected in the office, over the phone, or via mailer. The preoperative questionnaire contains the SANE, EQ-5D, Oxford Knee Score, and KOOS (The FJS and Patient Satisfaction questionnaires are only completed post-operatively). The postoperative questionnaire contains the SANE, Patient Satisfaction, FJS, EQ-5D, Oxford Knee Score, and KOOS validated patient administered outcomes scores.

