**G. Safety**

1. Adverse Events: Please reference section **6**, and section **15** for Adverse event data collection method and definitions. Only serious and device related adverse events will be collected for this study. Patient hospital readmissions should be documented on an adverse event form, and the relation to the device documented.
2. Revisions / Removals: Please reference section **4** and section **15** for Revision / Removal data collection method and definitions.
3. Withdrawals: Please reference section **3.4** for detailed data collection methods, and section **15** for relative definitions.
4. Protocol Deviations: Please reference section **5** for Protocol Deviation data collection methods for this study.

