**D. Subject Withdrawal Criteria:**

1. If patients meet any of the following criteria, a subject withdrawal form should be completed, and below data documented on the form:
  - a. Patient rescinds consent in writing: Date of occurrence
  - b. Patient Death: Reason and date of death should be documented, and any relation to study device.
  - c. Removal: Date of revision, all component part numbers removed, reason for revision, and any relation to study device.
  - d. Revision of Metal\* Components (Femur or Tibia): date of revision, all component part numbers removed, and reason for revision

*\*Bearing revisions in which only the polyethylene is replaced will not be withdrawn from the study.*

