### **4. REVISION / REMOVAL**

For subjects whom are revised in which a partial (revision) or full revision (removal) is conducted, an adverse event form should be completed. In patients in which metal or all components (removal) are removed, a withdrawal form should also be completed.

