### **6. ADVERSE EVENT MANAGEMENT AND REPORTING**

A record of all device related and serious adverse events, including details of the nature, onset, duration, severity, relationship to the device, relationship to the operative procedure and outcome, will be made on the relevant section(s) of the Adverse Event Form. The subject should be questioned about progress with previously reported adverse event(s) at each subsequent follow-up assessment visit. Definitions to be used for adverse event reporting are included in section 15. Any serious or unanticipated adverse events should be reported to the sponsor as soon as possible, as it is required to report unanticipated adverse events to the FDA within 10 days of knowledge of the event.

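### After year 2 no one is required to ask about new surgery on the study knee, so revisions done elsewhere may be missed and 10-year survivorship may be overstated

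*Combined protocol and SAP*

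**What the plan says.** **Objective.** Purpose C in section 1.4 reads "Evaluate patient perceived clinical outcomes and survivorship through 10-years of follow-up". Section 2.5 B lists survivorship among the secondary endpoints, and section 1.3 names it as a focus of the study.

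**Contact after year 2.** In Table 2.6-A the only item marked as required at 3, 5, 7 and 10 years is the PROMS questionnaire. Radiographs and the full Knee Society Score end at 2 years. Section 2.7 D says the same: "after the 2-year visit when the PROMS questionnaire is the only data point required". Section 2.7 F goes slightly further for the Knee Society Score: "After the 2-year visit, the patient administered portion will be collected with the PROMS Questionnaire by phone, email, or mailer from the patient".

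**Content of the contact.** Section 2.7 F states: "The postoperative questionnaire contains the SANE, Patient Satisfaction, FJS, EQ-5D, Oxford Knee Score, and KOOS validated patient administered outcomes scores". The footnote to Table 2.6-A gives the same instruments. Neither list includes an item on revision or reoperation.

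**Recording of events.** Adverse event and withdrawal forms are available as needed in every column of Table 2.6-A from the operation to 10 years. For a partial or full revision, section 4 says "an adverse event form should be completed", with a withdrawal form as well when metal or all components come out. For a removal, section 3.4 D lists what to document: "Date of revision, all component part numbers removed, reason for revision, and any relation to study device". On readmissions, section 2.7 G says "Patient hospital readmissions should be documented on an adverse event form, and the relation to the device documented".

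**Asking about events.** The one instruction on questioning patients is in section 6: "The subject should be questioned about progress with previously reported adverse event(s) at each subsequent follow-up assessment visit".

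**Analysis.** Section 8 gives no time-to-event method, event definition or censoring rule for survivorship.

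**The concern.** A survivorship estimate needs two things for each knee: the date of any revision, and otherwise the latest date on which the knee was known to be unrevised. Through year 2 the clinic visits and films can supply both. After that the required contact is a set of outcome scores that can be returned by mail, and a completed set does not show whether the implant is still the one that was put in.

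Take a patient whose study knee is revised at another hospital in year 4 and who mails back the year-5 questionnaire. The protocol requires the revision to be recorded, but gives the site no stated means of learning about it. If the site does not hear of it by some other route, the event is absent from the data. An analyst who treats knees without a reported revision as unrevised will then overstate survivorship. At stake is the credibility of the long-term estimate, which is the reason for following patients beyond year 2. Revision of a knee implant is uncommon enough that a few missed events make up a visible share of the total.

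**Working it through.** **Does any provision require asking?**

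- Sections 2.7 G, 3.4 and 4 say what to document once a revision, removal, reoperation or readmission is known. They do not say how a site finds out about one performed elsewhere.
- Section 6 calls for a record of all serious and device-related events, but describes questioning only for events already reported.
- Section 9 has a monthly review of completeness of the required milestones. A returned PROMS form satisfies the milestone at 3, 5, 7 or 10 years.
- Section 13 provides for monitoring of data quality, and section 11.1 for an annual summary of revisions and reoperations. Both work on what has been entered.
- Section 7 asks for explants to be returned, which depends on the hospital that removes them.

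No provision requires a question to every patient, a records search or a registry link. Capture after year 2 is passive.

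**Size.** The documents state no figure for survivorship. The sample size in section 8.1 (137 per group, 153 after allowing for loss) concerns the primary endpoint and does not bear on this point.

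From the documents: 306 knees, 153 per group. Assumed, because the documents are silent: 5% revised by 10 years, three fifths of these after year 2, and 10% to 40% of the later ones missed.

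- All revisions: 306 × 0.05 = 15.3
- After year 2: 15.3 × 3/5 = 9.2
- Missed: 9.2 × 0.10 = 0.9, up to 9.2 × 0.40 = 3.7
- Share of all revisions: 0.9/15.3 = 6%, up to 3.7/15.3 = 24%
- Share of all knees: 0.9/306 = 0.3 points, up to 3.7/306 = 1.2 points

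The last line is a simple proportion. It ignores deaths and losses and counts each missed knee as surviving.

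**Sensitivity to the assumptions.** Let r1 be the proportion revised in years 0 to 2, all captured. Let r2 be the proportion of the remaining knees revised in years 2 to 10, and m the share of those that is missed.

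True 10-year survivorship = (1 − r1)(1 − r2)
Observed = (1 − r1)(1 − r2(1 − m))
Overstatement = (1 − r1) × r2 × m

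With r1 assumed at 2%:

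| r2 | True survivorship | Overstatement, m = 10% | Overstatement, m = 50% |
|---|---|---|---|
| 2% | 96.0% | 0.2 points | 1.0 points |
| 3% | 95.1% | 0.3 points | 1.5 points |
| 5% | 93.1% | 0.5 points | 2.5 points |
| 8% | 90.2% | 0.8 points | 3.9 points |

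Across this grid, 0.3 to 6.0 revisions are missed per 153 knees. With m = 0 the overstatement is zero.

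**Comparison between arms.** Suppose r2 is 8% in one arm and 3% in the other. The true difference is 0.98 × (0.08 − 0.03) = 4.9 points. If half the late revisions are missed in both arms, the observed difference is 0.98 × (0.04 − 0.015) = 2.45 points. Equal under-capture shrinks a real difference and does not create one. A spurious difference needs capture to differ by arm.

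**The case against.** The strongest reply is that the protocol does not abandon safety follow-up at year 2. Forms stay open to year 10, any known revision must be recorded with its date and components, readmissions must be reported, and some contacts will be by phone, where a revision may well come up. This stands, and it rules out several stronger readings.

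- *That late revisions elsewhere will go uncounted and survivorship is overstated.* The documents support only that this may happen. They give no revision rate and no share treated elsewhere, and with no censoring rule nothing says that an unreported revision is counted as a surviving knee.
- *That a revision triggers no form.* It does, under sections 3.4 and 4. What is missing is a stated way to learn of it.
- *That section 6 restricts questioning to known events.* It requires a record of all serious and device-related events and does not forbid asking about new ones. It simply does not require it.
- *That knee scoring ends at 2 years.* Section 2.7 F continues the patient-administered part. Nothing there indicates a revision item.
- *That the questionnaire certainly lacks the question.* The case report forms are not in the documents, so the inference rests on the two lists of instruments.
- *That the comparison between arms is biased.* No provision suggests that capture would differ by device.
- *That the late PROMS are broadly contaminated by revised knees.* Section 3.4 keeps patella and polyethylene replacements in follow-up by design. Only missed metal revisions or removals would put scores in the data that should have stopped.

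None of this supplies an active check. A phone call may reveal a revision, but only by chance.

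**Conclusion.** The point holds in conditional form. After year 2 the plan relies on sites happening to hear of revisions performed elsewhere, while it promises survivorship through 10 years. Missed revisions would push the estimate upward if those knees are analysed as unrevised.

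The likely size is modest: 1 to 4 of 306 knees, or 0.3 to 1.2 percentage points, under the assumed 5% revision, three fifths after year 2 and 10% to 40% missed. The wider grid runs from 0.2 to 3.9 points. All of these rates are assumptions, so the direction is better supported than the size. The effect falls on a secondary endpoint. It is still worth correcting, because the remedy is cheap and a revision not asked about at the time may be hard to recover years later.

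**What to change.** Add one item to the 3-, 5-, 7- and 10-year contacts, asking whether the study knee has had another operation or any part replaced since the last questionnaire, with the date and hospital if so. State in sections 2.7 G and 4 that a yes triggers the adverse event form, and the withdrawal form where section 3.4 D applies. In section 8, define the survivorship event, name a time-to-event method, and censor each unrevised knee at the last date it is known to be unrevised, which the new item supplies.

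The cost is one question on an existing form, one database field and a minor amendment. The downside is that sites must follow up the yes answers. If the case report form already contains such an item, no new question is needed: the protocol should cite it and tie it to these forms and to the censoring date.

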**E. Clinical Assessments**

1. **Intra-operative Data:**
  - a. An operative record will be completed to record details of each operative procedure and of the used implants. Operative room procedure time, tourniquet time, components used, and Intraoperative complications will be recorded on the operative record.

**F. Clinical Outcomes**

1. Data to determine the clinical and functional performance of the device will be collected. Pre-operative and post-operative analysis will be compared using recognized and validated systems:
  - a. **Modified Knee Society Score**
    - i. The American Knee Society Score is part clinical exam and part patient administered assessment of the knee. The objective part of the score, also known as the "knee score," should be collected in the clinic by qualified personnel. The functional and pain scores can be collected in

the clinic or via phone or mailer. An additional assessment of the incidence of “anterior knee pain” has been added to this CRF as an exploratory endpoint but does not affect the score. The full score will be collected preoperatively and at each post-operative visit through 2-years. After the 2-year visit, the patient administered portion will be collected with the PROMS Questionnaire by phone, email, or mailer from the patient.

b. Patient Reported Outcome Measures “PROMS”

- i. A PROMS Questionnaire will be completed by the patient before surgery, and at each postop appointment indicated in the data collection table to assess the patient’s perception of their knee replacement. This survey can be collected in the office, over the phone, or via mailer. The preoperative questionnaire contains the SANE, EQ-5D, Oxford Knee Score, and KOOS (The FJS and Patient Satisfaction questionnaires are only completed post-operatively). The postoperative questionnaire contains the SANE, Patient Satisfaction, FJS, EQ-5D, Oxford Knee Score, and KOOS validated patient administered outcomes scores.

**G. Safety**

1. Adverse Events: Please reference section **6**, and section **15** for Adverse event data collection method and definitions. Only serious and device related adverse events will be collected for this study. Patient hospital readmissions should be documented on an adverse event form, and the relation to the device documented.
2. Revisions / Removals: Please reference section **4** and section **15** for Revision / Removal data collection method and definitions.
3. Withdrawals: Please reference section **3.4** for detailed data collection methods, and section **15** for relative definitions.
4. Protocol Deviations: Please reference section **5** for Protocol Deviation data collection methods for this study.

**H. Radiographic Assessments (including Radiographic Assessment protocol)**

1. Views
  - a. Standard Anterior-Posterior (AP)
  - b. Standard Lateral View

- c. Skyline merchant's view
- d. Standing alignment (Long leg)

2. Placement

- a. The X-ray should show the total prosthesis including the entire length of the femoral and tibial stem.

3. Radiographic Collection Periods

- a. 0 to 12 weeks postoperative as baseline
  - i. Standing Long Leg AP
  - ii. Standard Short Films (AP, ML, Skyline)
- b. 1 Year Follow-up
  - i. Standard Short Films (AP, ML, Skyline)
- c. 2 Year Follow-up
  - i. Standard Short Films (AP, ML, Skyline)

4. Radiographic Assessment Form

A radiographic assessment form will document the radiographic findings for each patient in this study. The 0-12 week films are to be used as baseline radiographic data for subsequent follow-up assessments / comparisons at 1 and 2 years post-op.

- a. Standing AP Long Leg Film: A standing long leg x-ray will be taken at 0-12 weeks in addition to standard films in order to document mechanical leg alignment.
- b. Standard Short Films:
  - i. Assessments will be done according to the Knee Society Total Knee Arthroplasty Roentgenographic Evaluation for:
    - 1. Alignment of components - (Standard Films)
    - 2. Radiolucent lines (RLL) - (Standard Films)
  - ii. Migration/Subsidence – (Standard Films)
- c. If any osteolysis (a radiolucent line greater than 2mm in two or more zones that was not present on the 0-12 week x-ray) or gross shifting or migration of components (movement greater than 3mm or greater than 3 degrees as compared to the 0-12 week x-ray) is noted, it should be documented on a adverse event form.

**2.8. ALLOWED WINDOW OF EACH SCHEDULE**

## A. Allowed Window of Each Schedule:

1. Discharge: 0-12 weeks
2. 6 months (+/- 2 weeks)
3. 1 year (+/- 2 months)
4. 2 years (+/- 2 months)
5. 3 years (+/- 2 months)
6. 5 years (+/- 2 months)
7. 7 years (+/- 2 months)
8. 10 years (+/- 2 months)

B. Each follow-up visit time point will be determined based on the date of surgery. All efforts should be made to bring patients back within the follow-up windows. Because this is a post-market study long-term study, patient visits that fall outside of window are allowable and will not be considered protocol deviations. The impact of the visit date will be assessed during data analysis.

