### STUDY SUMMARY

TITLE	Randomized Controlled Clinical Outcomes of the Vanguard XP Bicruciate Knee System
DESIGN	Prospective Controlled Multi-Center
PURPOSE	Compare the clinical outcomes of the Vanguard XP Bicruciate Total Knee System to the Vanguard CR Total Knee System
OUTCOME MEASURES	Patient Perception of recovery, Operative Room Procedure Time, Intraoperative complications; Anterior Cruciate Ligament (ACL) status; knee stability; readmissions, adverse events, pain, patient satisfaction, quality of life
POPULATION	306 knees, 5 surgeons
ELIGIBILITY	Patients will be included according to FDA cleared labeling of device in accordance with indications and contraindications for use.
DURATION	The study is anticipated to last no longer than 12 years which will include time for enrollment, data collection through ten years of follow-up and data analysis.

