## 2.6. ASSESSMENT PROCEDURE

**Table 2.6-A**

Form	Pre-op (screening)	Operative (Enrollment)	Discharge	3 Mos	6 Mos	1 Yr	2 Yrs	3 Yrs	5 Yrs	7 Yrs	10 Yrs
Screening Log	X										
Informed Consent	X										
Demographics / Medical History	X										
Operative Form		X									
Modified Knee Society Score*	X		X	E†	SC***	X	X				
PROMS** Questionnaire	X		X	E†	SC***	X	X	X	X	X	X
Radiographs: AP, ML, Skyline			X	E†	SC***	X	X				
Radiographic Form			X			X	X				
Adverse Events		AS NEEDED	AS NEEDED	AS NEEDED	AS NEEDED	AS NEEDED	AS NEEDED	AS NEEDED	AS NEEDED	AS NEEDED	AS NEEDED
Withdrawals		AS NEEDED	AS NEEDED	AS NEEDED	AS NEEDED	AS NEEDED	AS NEEDED	AS NEEDED	AS NEEDED	AS NEEDED	AS NEEDED
Protocol Deviations		AS NEEDED	AS NEEDED	AS NEEDED	AS NEEDED	AS NEEDED	AS NEEDED	AS NEEDED	AS NEEDED	AS NEEDED	AS NEEDED

\*Modified Knee Society Score includes an additional assessment of incidence of anterior knee pain. This additional question is exploratory and will not affect the total score of the KSS. In the event that a patient does not return for a visit, a partial “Phone Knee Society Score” can be completed and entered into the database.

\*\*Patient Administered Outcome Scores “PROMS” Questionnaire can be collected in the office, over the phone, or via mailer. The questionnaire contains SANE/Patient Satisfaction, Oxford Knee Score, EQ-5D, KOOS, and the Forgotten Joint Score validated patient administered outcomes scores. These scores are combined into the paper version for easier administration to patients for completing. When entering to Joint Assist, these scores will be separated but contain the same exact questions.

\*\*\*SC: 6 Month visit should be collected only if standard of care. Radiographs should be taken if standard of care at the center, however no radiographic form will be collected. Any adverse event or failure determined from radiographs should be documented on an adverse event form. All visits will be documented relative to the clinical site in the approved informed consent.

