†"E" = exploratory and not required. If centers choose to collect 3-month data, they may although it is not required of this protocol. It should only be collected at centers where it is standard of care as an exploratory measure. Biomet will not reimburse for this milestone, but will allow data storage for centers that choose to document this to follow all standard of care visits. If this visit is followed, it must be included in the informed consent.

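### The only early PROMS and Knee Society Score required of every site falls anywhere in a 0-12 week window with no stated adjustment for timing, so the early comparison is less precise than it need be

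*Combined protocol and SAP*

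**What the plan says.** Table 2.6-A requires the modified Knee Society Score, the PROMS questionnaire and radiographs at the visit labelled Discharge. Section 2.8 A gives that visit the window "Discharge: 0-12 weeks".

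The two visits that follow do not bind all sites. The 3-month visit is "exploratory and not required" and has no window in section 2.8. For the other, the table note says "6 Month visit should be collected only if standard of care". The next follow-up required everywhere is at 1 year, with a window of 2 months either side.

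Section 2.8 B states that "Each follow-up visit time point will be determined based on the date of surgery". It accepts out-of-window visits without counting them as deviations, and undertakes to look at the effect of visit date when the data are analysed. It names no method. For continuous secondary outcomes, section 8.3 offers a choice of unadjusted comparisons: a t-test, one-way ANOVA or a Wilcoxon test.

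Section 2.7 H uses the 0-12 week films as the radiographic baseline. Section 9 counts the 0-12 week visit as part of a complete enrollment. The notes to Table 2.6-A say that the PROMS "Questionnaire can be collected in the office, over the phone, or via mailer".

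**The concern.** The label and the window point to different times. One site can hand out the Forgotten Joint Score, satisfaction and KOOS forms as the patient leaves hospital, another can do so at week 12, and both have completed the same milestone. Section 2.7 H gives a reason for a wide window for films. The documents give none for scores that are likely to change while the patient recovers.

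What is at stake is any between-arm comparison at this visit. PROMs, pain relief and function are secondary endpoints in section 2.5, and the outcome list in the study summary opens with "Patient Perception of recovery, Operative Room Procedure Time, Intraoperative complications". If timing varies widely, the spread of scores grows and a real early difference is harder to see. If timing also differed by arm, part of an observed difference would reflect the calendar rather than the implant.

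**Working it through.** **The plan's own figure.** The only computed figure is the primary sample size in section 8.1: proportions 0.66 and 0.83, two-sided alpha 0.05, power 90%. With pooled variance under the null and no continuity correction:

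n = [1.960 × √(2 × 0.745 × 0.255) + 1.2816 × √(0.66 × 0.34 + 0.83 × 0.17)]² / 0.17² = (1.208 + 0.775)² / 0.0289 ≈ 136.1, so 137 per group. Then 137 / 0.90 = 152.2, so 153. Both figures reproduce, and nothing below alters them.

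**Inputs for the early visit.** The window is 12 weeks (section 2.8 A) and allocation is 1:1 (section 2.4). The documents give no SD, recovery slope or timing distribution for early scores, so these are assumptions:

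- Scores at a fixed time have SD 1, and the mean improves linearly by G of those SDs over 12 weeks. G is taken from 0.5 to 2.
- There are 137 evaluable knees per arm, borrowed from section 8.1 and treated as independent.
- The reference effect has 90% power at a fixed time: (1.960 + 1.2816) × √(2/137) = 0.39 SD.

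**Case 1: same timing in both arms.** Visits spread evenly over 12 weeks add variance G²/12, so the variance factor is 1 + G²/12. Power is Φ(3.2415/√factor − 1.960). If half the visits fall at day 0 and half at week 12, the factor is 1 + G²/4. With an even spread over a 4-week window (+/- 2 weeks), it is 1 + (G/3)²/12.

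| G (SD) | Even over 0-12 wk: factor, power | Half day 0, half wk 12: factor, power | Even over 4 wk: factor, power |
|---|---|---|---|
| 0.5 | 1.021, 89.4% | 1.0625, 88.2% | 1.002, 89.9% |
| 1 | 1.083, 87.6% | 1.250, 82.6% | 1.009, 89.7% |
| 1.5 | 1.188, 84.5% | 1.5625, 73.7% | 1.021, 89.4% |
| 2 | 1.333, 80.2% | 2.000, 63.0% | 1.037, 88.9% |

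In each of these rows the expected timing contribution is the same in both arms and cancels from the difference. The cost is variance, not bias.

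**Case 2: timing differs by arm.** If one arm is seen w weeks later on average, the false difference is G × w/12 SD. For w = 2 it is 0.08, 0.17, 0.25 and 0.33 SD for the four values of G. With no true difference, SD √(1 + G²/12) and 137 per arm, the chance of a significant result is 10.5%, 26.3%, 47.6% and 66.6%. For w = 1 it is 6.3%, 10.2%, 15.8% and 22.3%. These gaps are illustrative; the documents report no difference in timing.

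**Can timing differ by arm?** Section 2.4 describes blinding for the patient alone, ending at surgery. Section 2.8 B does not enforce windows. So nothing prevents it, and nothing shows that it happens.

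**The case against.** The strongest reply is that this visit carries little weight. No primary or secondary endpoint in section 2.5 is attached to it. The purposes in section 1.4 concern a knee that feels normal, outcomes through 2 years, and perceived outcomes and survivorship through 10 years. Section 14.2 speaks of recovery in general terms, so its appearance in the summary need not mean early speed. These points stand, and they keep the concern modest.

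A second reply is that randomization protects the comparison. A reader might infer that a 0-12 week window makes the early scores useless for comparing arms. The documents do not support that: both arms share one window, and the example of two sites with different habits is variation between sites, not between arms. A reader might also infer that unblinded sites will see one arm later. That is possible but undocumented.

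A third reply is that section 2.8 B already covers visit date, and that days since surgery can be derived because visits are timed from surgery. Under the linear model above, that covariate would remove both the added variance and the bias. This stands in part. Section 2.8 B commits to no method and section 8.3 contains no adjusted model. The true recovery curve need not be linear. If timing follows local practice, it is also entangled with the center's rehabilitation and expectation management, which section 2.7 C records at center level only. Adjustment helps, but it is weaker than collecting the forms at a common time.

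Finally, the sizes rest on assumed slopes. At 0.5 SD the loss is almost negligible with evenly spread visits.

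**Conclusion.** The concern holds as a loss of precision in early comparisons, with a conditional exposure to bias. With visits spread evenly and alike in both arms, and improvement of 0.5 to 2 SD over 12 weeks, variance rises by 2% to 33% and power for an effect that would have 90% falls to between 89% and 80%. The extreme half-and-half split would take power to 63% at the steepest slope. Bias requires timing to differ by arm, so the figures for that case show sensitivity and are not a prediction.

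A reader might go further and infer that the primary analysis or the 306-knee sample size is compromised. Neither follows, because the sample size reproduces and does not use this visit. Section 2.5 names no time point for the primary endpoint. That is a separate gap, but timing would matter more if this visit were ever used for the primary endpoint.

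This is an inexpensive improvement to the plan, not a flaw that threatens its main conclusions.

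**What to change.** 1. In section 2.8 and Table 2.6-A, split the milestone. Keep 0-12 weeks for the baseline films and radiographic form. Give the early PROMS one target time, chosen by the sponsor and common to all centers, with a window of about +/- 2 weeks. The phone and mail routes already allowed make this workable. If the window is kept in practice, the table above puts the remaining added variance at 0.2% to 3.7%.
2. Replace the general undertaking in section 2.8 B with a prespecified early comparison of PROMS and Knee Society Score, adjusted for days since surgery, and add it to section 8.3. The objective part of the Knee Society Score needs a clinic visit, so it may stay on the wider window and relies more on this adjustment.
3. Report the distribution of visit timing by arm, so that any imbalance is visible. This matters because windows are not enforced.

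The cost is small. Some PROMS forms must be mailed or phoned apart from the clinic visit. The complete-enrollment wording in section 9 and the site consent text need matching minor changes, with IRB approval of the amendment under section 14.3.
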